Fasting venipuncture and assays. Phlebotomy will be performed using standard techniques by trained staff following a written protocol, for withdrawal of 20 cc of blood. The phlebotomist will draw two 10 ml EDTA plasma tubes for this protocol. Pre-labeled, bar coded tubes will be used for specimen tracking. After venipuncture, the blood tubes will be incubated at room temperature for 30 minutes before being spun in a centrifuge, aliquoted and frozen. Samples will be placed into an at least $-20^{\circ}\text{C} \pm 10^{\circ}\text{C}$ freezer within 90 minutes from venipuncture time. The samples will be transferred into the final freezer (-80°C) within 24 hours.

Serum PIIIINP will be measured in [name] laboratory using a commercially available radioimmunoassay (UniQ PIIIINP RIA, Orion Diagnostica). This is a quantitative radioimmunoassay of intact aminoterminal propeptide of type III procollagen in human serum, which will be used to detect changes in connective tissue metabolism. Plasma NT-proBNP will also be measured in [name] lab, using a commercially available ELISA kit (Alpco Diagnostics, Salem, NH). Serum isoprostanes will be measured in [name] laboratory using a commercially available ELISA (Cayman Chemical, Ann Arbor, MI). TNF α and IL-6 will also be measured in [name] laboratory, using a commercially available ELISA (R & D Systems Inc., Minneapolis, MN) for TNF α and an Access Chemiluminescent Immunoassay (Beckman Coulter, Fullerton, CA) for IL-6. Hs-CRP will be measured in the clinical laboratory at the VA Boston Healthcare System.

Echocardiogram. Standard transthoracic 2-dimensional and Doppler echocardiography will be performed using a Philips IE33 cardiac ultrasound (Philips Healthcare, Andover, MA) to estimate cardiac dimensions, mass, and systolic and diastolic function. All images will be captured in 3-beat loops for patients in sinus rhythm, 5-beat loops for those in atrial fibrillation. M-mode measurements of LV dimensions will be performed and analyzed according to the American Society of Echocardiography recommendations (61). LVEF will be measured using the modified Simpson's method. The interventricular septum thickness (IVST), posterior LV wall thickness (LVPWT), and left ventricular internal diastolic diameter (LVIDD) will be measured at end-diastole, and left ventricular mass calculated as $0.8*(1.04*[(\text{LVIDD}+\text{IVST}+\text{LVPWT})^3-(\text{LVIDD})^3]+0.6)$. We will determine standard measures of diastolic function including E and A wave velocities, deceleration time, and pulmonary venous flow velocities, as well as utilize tissue Doppler imaging to detect abnormalities of diastolic function. Pulmonary artery systolic pressure will also be estimated utilizing Doppler measurements. For individuals with unclear images, or who have required contrast in the past, contrast will be used.

Cardiopulmonary Exercise Testing. Treadmill exercise testing in association with air-gas-exchange, generally considered to be an optimal gauge of functional capacity, will be supervised by [name] (co-investigator), who has used this technique extensively in both clinical and clinical-research applications. All patients will be assessed by a cardiologist for clinical stability immediately before the exercise stimulus. An intravenous catheter will be placed in advance of the procedure per routine as a routine safety precaution. A motor-driven treadmill will be used and exercise will follow a modified Balke protocol. A bicycle ergometer will be used for those participants who are unable to walk on a treadmill but are capable of bicycle exercise (e.g., due to balance problems). A lightweight disposable pneumotach

device will be positioned in the participant's mouth during the exercise VO₂ peak, VO₂ at anaerobic threshold and VE/VCO₂ will be measured using a metabolic cart. During exercise, electrocardiogram waveforms and hemodynamics (maximum heart rate and blood pressure) will be monitored. Patients will exercise to their symptomatic limits, with encouragement to achieve a respiratory exchange ratio >1.0 (consistent with high physiological workload). However, if there are any signs of medical instability, the cardiologist will end the test before the symptomatic endpoint is achieved. In any instances of submaximal workload, analysis would focus on VO₂ at anaerobic threshold, VE/VCO₂ and other indices that do not depend on peak exercise performance.

Questionnaires

- Medical Outcomes Study SF36 Health-related Quality of Life Questionnaire. Each subject will complete the SF36 at their baseline and 3 month follow-up appointment. This questionnaire is a multi-purpose, short-form health survey that is widely used in research to estimate specific disease burden and to compare disease-specific benchmarks with general population norms. The questionnaire consists of 36 questions and provides an 8-scale profile of functional health and well-being scores (62).
- Kansas City Cardiomyopathy Questionnaire. Each subject will complete this questionnaire at their baseline and 3 month follow-up appointment. This questionnaire is widely used to evaluate quality of life in heart failure patients. It consists of 23 items which assess the level of impact of physical symptoms in this population such as shortness of breath, fatigue, peripheral edema, and difficulty sleeping. It also assesses the impact of psychological symptoms like anxiety and depression, as well as social functioning (63).
- CHAMPS Physical activity questionnaire for older adults (64). Each subject will complete this questionnaire at their baseline and 3 month follow-up appointment. This questionnaire is used to assess physical activity in our population.
- Health Questionnaire. Each subject will complete this questionnaire at their baseline and 3 month follow-up appointment. This questionnaire is used to collect data about medical history, and general but important health indicators, e.g., alcohol use, sleep quality, and restless leg symptoms.

Ambulatory Blood Pressure Monitoring. Participants will be instructed in the use of an Ambulatory Blood Pressure monitor. The device consists of a blood pressure cuff that is connected by rubber tubing to a small pressure monitoring device that weighs only 9 oz and fits easily in a shirt pocket. The device will be programmed to measure BP at 20 minute intervals during the day and 30 minute intervals at night (11 PM to 7 AM) for the subsequent 24 hours. A pre-paid addressed box will be provided for mail return of the device.

Randomization. After completing testing at the baseline visit, and being instructed in the use of the ambulatory blood pressure monitor, participants will be randomly assigned in a 1:2:2 ratio to one of three treatment groups: **Healthy Lifestyle and Sleep Education** alone (HLSE); HLSE plus Continuous Positive Airway Pressure (CPAP); or HLSE plus nocturnal supplemental oxygen (NSO). Randomization will be performed using permuted blocks, stratified by recruitment site. A SAS program will be used to generate two separate lists of randomization assignments for the two strata. These lists will be

placed into a single data table in a Microsoft SQL Server 2008 database to serve as a lookup table. When a new participant record is created in the database, a trigger is fired on the SQL Server randomization data table that looks up the corresponding stratum using predominant sleep apnea type, picks the next assignment from that stratum, updates the lookup table with the Study ID randomized and the date/time of randomization. Due to the nature of the treatments, blinding of subjects to treatment arm is not possible. The ultrasonographers and physicians overseeing and scoring the echocardiograms and cardiopulmonary exercise tests will be blind to treatment assignment.

Treatment

Healthy Lifestyle and Sleep Education (HLSE Group)

Research Staff at each site will provide counseling on sleep hygiene and general heart healthy lifestyle using a slide show developed for this purpose. The presentation will suggest non-pharmacologic approaches to improve the regularity and duration of sleep, aiming for 7-8 hours of sleep per night. General lifestyle advice relevant to sleep apnea will also be provided, including a recommendation for weight loss and regular exercise as tolerated, per American College of Cardiology/American Heart Association guidelines (26), and avoidance of smoking, excessive alcohol consumption, and use of illicit drugs. The importance of adherence to prescribed medical regimens will also be emphasized. The slides and written materials will be provided to participants at the baseline visit and reviewed at the one-week telephone contact. All participants will have had clinical management reviewed by a study physician to ensure adherence to current HF treatment guidelines, as described above.

Healthy Lifestyle and Sleep Education plus CPAP (CPAP Group)

In addition to HLSE, this intervention includes sleep apnea treatment with continuous positive airway pressure (CPAP). The CPAP device to be employed in this study is the AutoSet Med S9 (Resmed, San Diego, CA). Participants will be educated on the use of the CPAP device, targeting self-efficacy and cognitions related to CPAP. Participants will have an opportunity to try various mask interfaces in order to optimize fit. Verbal and written directions on the use of these materials will be provided, with instructions reinforced at interim telephone follow-up calls.

Participants randomized to the CPAP Group will then be scheduled for CPAP titration in the Sleep Laboratory of the VA Boston or VA Connecticut Healthcare System. All technicians in both Sleep Laboratories are Registered Polysomnography Technicians who are credentialed for human subjects research and have experience in the administration and titration of CPAP. CPAP titration will be performed overnight on a single night in the Sleep Laboratory. Participants will undergo polysomnography with a typical montage according to current American Academy of Sleep Medicine recommendations, including electroencephalogram, electro-oculogram, chin electromyogram, respiratory inductance plethysmography, finger pulse oximetry, leg electromyogram, and electrocardiogram. Airflow and mask pressure will be monitored and recorded from the CPAP device. Participants will be habituated to the preferred mask prior to study initiation. The CPAP device will be set to deliver pressure starting at 4 cm H₂O pressure. The CPAP pressure will be increased in increments of 1 cm H₂O, at intervals of no less than 10 minutes, in order to eliminate both obstructive and central apneas, with a maximum CPAP pressure of 20 cm H₂O.

The Research Coordinator will maintain contact with participants by telephone during

the first 7 days of CPAP treatment to assist with any troubleshooting. The CPAP device is capable of wireless transmission of utilization and efficacy data. At the end of the first week of CPAP use, and again at weeks 2, 4 and 8 (in advance of each scheduled interim telephone contact), the utilization data will be reviewed by the Research Coordinator who will judge their acceptability based on usage for at least 4 hours/night for at least 5 nights and absence of excessive mask leak. If adherence does not meet these targets, the Research Coordinator will discuss with the participant in an attempt to overcome barriers to adherence.

Healthy Lifestyle and Sleep Education plus Nocturnal Supplemental Oxygen (NSO Group)

In addition to HLSE, this intervention includes nightly treatment with nocturnal supplemental oxygen (NSO). Oxygen therapy will be initiated at 2 lpm via nasal cannula, with routine clinical follow-up using overnight oximetry to assess adequacy of this flow rate. If needed, oxygen will be increased in 1 lpm increments as needed to (1) maintain baseline saturation >90%, and (2) to reduce the frequency of 3% oxyhemoglobin desaturation events to <5 per hour (independent of baseline saturation level). As oxygen at 2 lpm via nasal cannula has been shown to reduce the number of 4% desaturations during sleep in patients with sleep apnea by 89%, we anticipate that most participants will be adequately treated at 2-4 lpm. Oxygen is provided by a stationery oxygen concentrator. Adherence with oxygen use is measured by hours of machine use over the intervention period.

Interim telephone contact

Following initiation of therapy, study staff will make telephone contact with each participant at weeks 1, 2, 4 and 8 to identify any early problems with treatment adherence and to ascertain any adverse events. In particular, sleepiness will be re-assessed using the Epworth Sleepiness Scale and [name] or [name] will contact any patient whose Epworth Sleepiness Scale score is ≥ 16 or who provides a response of 2 or 3 on the item regarding drowsy driving. At week one the Healthy Lifestyle Education will be presented to each group over the phone in conjunction with education materials set home with patient at baseline visit.

Final study visit

After 12 weeks of intervention, participants will return for a final study visit at which time all procedures performed at the baseline visit will be repeated, including phlebotomy, echocardiography, cardiopulmonary exercise testing, and questionnaire administration. Participants will be asked to complete, while wearing the assigned therapy 24-hour ambulatory blood pressure monitoring.

Following completion of study procedures, each participant will be encouraged to accept referral to a sleep specialist within the VA to discuss treatment of sleep apnea.

Statistical analysis

This study is a randomized clinical trial with three parallel treatment groups, designed to compare the active treatment groups (CPAP and NSO) to the optimal medical management comparator (HLSE). Baseline data will be summarized using standard descriptive statistics for demographic and baseline clinical characteristics by treatment group. Based on our experience with the HeartBEAT Study, the rate of dropouts during the course of the three-month trial is expected to be low and we do not expect dropouts

to be differential with respect to treatment group assignment. The main analysis will include all subjects completing the follow-up examination. For the purposes of a sensitivity analysis, a result of “no change” will be imputed for all drop-outs, and compared to the main analysis.

The analysis for each of the primary outcome measures (LVEF and peak VO₂) will consist of a one-factor analysis of variance comparing the mean changes from baseline in LVEF (or VO₂). As we postulate similar benefits from CPAP and NSO, we will specify two contrasts: CPAP vs. HLSE and NSO vs. HLSE as our primary analyses. In a secondary analysis, we will also compare the effects of CPAP to NSO for the purpose of hypothesis generation for subsequent larger studies. This analysis is a simple analysis of variance, with data transformation or adoption of rank-based inference if approximate normality is not present. While the randomization should achieve approximate balance on potentially confounding conditions, analysis of covariance models that employ adjustments for recruitment site, age, sex, sleep apnea severity, comorbid illness, smoking and alcohol use will be fit to potentially improve the efficiency of the treatment effect estimates. Should a significant difference between treatment and comparator be identified, further exploratory analyses will assess the relation of adherence to therapy to change in outcome measures.

In order to compare the effectiveness of the assigned interventions in controlling sleep apnea over the course of the study, an additional exploratory analysis will compare the change in AHI, change in time in periodic breathing, and change in time at SpO₂ <90% between the baseline and final portable sleep monitoring studies. This analysis will utilize a one-factor analysis of variance. Further exploratory analyses will assess the relation of effectiveness of control of sleep apnea to changes in the primary outcome measures.

This study provides an opportunity to evaluate multiple intermediate measures that might shed light on the mechanism of benefit of CPAP or NSO. These analyses are considered exploratory in nature. As each of the secondary outcome measures is continuous, analysis of these variables will be treated in a similar fashion to the analysis of the primary study endpoints. For analysis of blood pressure, the 24-hour mean blood pressure and the ratio of mean nighttime to mean daytime blood pressure will also be analyzed.

Mean hours of use of therapy over the 3-month intervention period between CPAP and NSO groups will be compared using a one-factor analysis of variance, with appropriate modification as needed for deviation from normality. The number of adverse events and serious adverse events in each per study arm will be tabulated and categorized according to their severity, expectedness and relationship to the study intervention.

Sample size and power

Our primary goals are to establish the efficacies of CPAP and NSO compared to HLSE. Because past studies were suggestive of a more beneficial effect of CPAP or NSO compared to HLSE, we propose to randomize more subjects to the two experimental treatment groups. That is, we propose to allocate patients into CPAP, NSO or HLSE randomly according to a 2:2:1 ratio. This strategy also improves statistical power for the secondary comparisons between CPAP and NSO.

The sample size for this study was chosen to provide adequate power to detect a significant difference in LVEF between each treatment group and the control group (Aim

1). We have used effect estimates based on the meta-analyzed mean effect sizes for CPAP and NSO included in the AASM Practice Parameters paper (41) of 6.4%, and 5.0% for CPAP and NSO, respectively, and an estimated SD of change in LVEF of 4.8% based on previous reports of the effect of either ASV, CPAP or NSO (40, 42, 45-47) on LVEF in patients with sleep apnea. We use the Bonferroni method to account for 2 main comparisons and perform the test comparing each treatment to control at a 2.5% significance level. Using a two-sided two-sample t-test, an evaluable sample size of 34 in the NSO (or CPAP) group and 17 in the HLSE group will achieve 90% power to detect a difference of 5.0% with a significance level of 2.5% assuming a standard deviation of 4.8% in each group, and 98% power to detect a difference in LVEF of 6.4%; there will be 80% power to detect a difference as small as 4.4% between either active treatment group and the HLSE group.

Changes in peak V02 (Aim 2) will be compared in a similar fashion as changes in LVEF. An evaluable sample size of 34 in CPAP or NSO group and 17 in HLSE group will have 80% power to detect a difference of 0.92 standard deviations with a significance level of 2.5% using a two-sided two-sample t-test. Only one study of treatment of central sleep apnea in HF reports the SD of change in peak VO₂, which was 2.5 ml/kg/min (58). The reported change in peak VO₂ with treatment of central sleep apnea with NSO was 1.4-5 ml/kg/min, with a median of 2.5 ml/kg/min (47, 50, 55, 58). The power for this Aim therefore appears adequate.

For the exploratory comparison of CPAP and NSO, the sample sizes of 34 evaluable subjects per group will provide 80% power to detect a difference of 3.3% in change in LVEF, assuming a SD of change of 4.8% and a two-sided significance level of 5%.

As comparisons for secondary outcomes (Aim 4) are exploratory in nature, they will be performed at 5% significance level without multiple comparison adjustment. For comparisons in a continuous outcome between each treatment group and the control group, an evaluable sample size of 34 in CPAP or NSO group and 17 in HLSE group achieve 80% power to detect a difference of 0.84 standard deviations with a significance level of 5% using a two-sided two-sample t-test.

The proposed sample size of 39 in each active treatment group and 20 in the HLSE group includes a 15% increase over the needed number of evaluable subjects, to allow for expected rates on non-completion of the protocol.

Reasons for stopping assigned treatment

As there is clinical equipoise with respect to the long-term benefits of treatment of sleep apnea in chronic HF, and the duration of the intervention is short at 3 months, there is no plan to discontinue assigned treatment due to therapeutic failure related to cardiac disease. However, as treatment of sleep apnea may be expected to improve sleepiness, any participant who develops unsafe levels of sleepiness that in the opinion of the PI place him or her at increased risk of motor vehicle accidents or other safety risks, will be treated for their sleep apnea off protocol. While serious adverse effects of either CPAP or supplemental oxygen are not anticipated, should any serious adverse events occur that in the opinion of the PI are treatment related, the treatment will be discontinued.

Human Subjects Potential Risks

The study procedures do not place the subjects at risk of harm or discomfort greater than those encountered in routine medical care. The vein puncture for blood drawing is

associated with temporary pain at the time of needle insertion and may result in bruising at the needle insertion site. Rarely, fainting occurs with a blood draw. Portable sleep monitoring and ambulatory blood pressure monitoring may lead to minor sleep disturbance and some subjects may experience mild skin irritation from the sensors or electrodes used. Use of the blood pressure cuff may cause mild discomfort as the cuff is inflated. When the blood pressure cuff is worn for 24 hours, there may be some soreness in the arm. The administration of questionnaires may be stressful, although none ask sensitive information. The echocardiogram may cause transient discomfort as the ultrasound probe is pressed against the chest and upper abdomen. Cardiopulmonary exercise testing may cause shortness of breath, fatigue, muscle discomfort, and very rarely (<1:1,000) may be associated with heart attack or death. The intravenous (IV) catheter that will be placed for the exercise has a small chance of causing bruising or infection. Standard precautions will be followed in cleaning and sterilizing the area. If contrast is needed for the echocardiogram, there is a small chance of allergic reaction. There is a rare chance (1:10,000) that patients may be allergic to the microscopic bubble contrast (lipid shell and gas), thus allergies will be confirmed via patient medical charts and verbally with the patient prior to the injection of the contrast agent. Special efforts will be taken to reduce risks by watching each subject for 30 minutes after the echo contrast agent.

The study treatments are generally considered quite safe. CPAP is an FDA-approved therapy for the treatment of sleep apnea. Its use can be associated with a number of minor side effects, including nasal congestion, runny nose, dry nose or mouth, skin irritation from the mask or headgear, aerophagia or discomfort from the mask or air pressure. Rarely, sinus problems may get worse while using CPAP and mild nose bleeds may occur. Polysomnography will be performed for the purpose of CPAP titration in patients randomized to this therapy. This procedure is inconvenient, as it requires an overnight stay in the Sleep Laboratory, but poses no major risks. There may be some discomfort from placement of the sensors on the scalp and face, and wearing the sensors may cause sleep disruption. Occasionally there is discomfort or redness at the site of sensor placement. Rarely (<1:100) the skin irritation may require treatment with a topical steroid. Supplemental oxygen delivered through the nose may be associated with minor side effects such as discomfort from the nasal prongs, dry nose, nasal stuffiness, mild nose bleeds or skin irritation. The use of a saline nasal spray can help prevent dryness and nosebleeds. Although oxygen at the levels prescribed in this study is not known to be harmful, oxygen can increase the risk of fire. It is possible that patients randomized to optimized medical care alone or with NSO may not be effectively treated for their sleep apnea for the 3 months of the study. Untreated sleep apnea may place subjects at increased risk of motor vehicle and other accidents; however, in a study of 1105 patients with sleep apnea randomly assigned to CPAP or sham CPAP for 6 months (the Apnea Positive Pressure Long-term Efficacy Study), we had no episodes of motor vehicle accidents due to sleepiness using safety education and monitoring procedures similar to those of present study.

Protection against risks

All study personnel will be fully trained and credentialed in Human Subjects Protections. All research data will be collected on standardized research forms with de-identified ID numbers, without personal identifiers. Any data collected from medical records will be entered onto case report forms with only study ID numbers, excluding personal

identifiers. Only study personnel will have access to research data, which is kept either in locked cabinets, in password-protected computers in locked offices, or on secure password-protected drives located behind the VA firewall or at the Center for Clinical Investigation at Brigham & Women's Hospital. All personal data will be stored separately from de-identified research data, and will be stored in password-protected files behind the VA firewall or in locked cabinets within the VA. Blood and specimens will be stored using de-identified bar codes at the VA Boston and shipped to [name] laboratory, the VA Boston clinical lab for testing. Once the assays have been run on the samples, any leftovers will be destroyed.

Risks from cardiopulmonary exercise testing will be minimized by close physician supervision of testing, which will be performed by trained technicians in the Cardiopulmonary Exercise Laboratories at the VA Boston and VA Connecticut HCS sites, with emergency equipment readily available. Although patients will be encouraged to exercise to their symptomatic limits, if there are any signs of medical instability, the cardiologist will end the test before the symptomatic endpoint is achieved.

Phlebotomy will be performed by trained phlebotomists.

All CPAP devices will be equipped with heated humidifiers to minimize drying, and attention will be paid at set-up to identifying a best-fit mask to minimize mask discomfort and air leaks. Subjects will be contacted at weeks 1, 2, 4 and 8 to identify any early problems with treatment and to ascertain any adverse events, in particular the onset of dangerous levels of sleepiness. Participants will be extensively counseled at the baseline visit on safety measures related to excessive sleepiness. Participants randomized to NSO will be counseled on risks of fire from use of oxygen near open flames, including cigarettes.

Potential Benefits of the proposed Research to Human Subjects and Others

There are a number of potential benefits to participants. All participants who undergo sleep apnea screening will be provided information on the results of their sleep studies, which may be useful in further health management. Participants randomized to CPAP or oxygen may experience direct benefit related to treatment of underlying sleep apnea. There are also potentially important benefits to others, if the study identifies a well-tolerated alternative to positive pressure ventilation to reduce cardiac risk in the many patients with chronic heart failure and sleep apnea. As the risks to individual participants are small, and the potential benefit large, the risks of participation in the study are justified.

Importance of the knowledge to be gained

The societal benefits to the study include the generation of pivotal data for designing a definitive study that will for the first time address the relative effectiveness of alternative approaches to treatment of a very common comorbid illness (sleep apnea) in patients with heart failure. The approaches proposed may significantly reduce the costs and burden of current diagnostic and treatment approaches and improve access to treatment for a high risk population. The study may also provide important insights into the mechanism of the adverse cardiac effects of intermittent hypoxemia and sleep apnea, thereby stimulating research into additional novel therapies.

Literature Citations (as applicable).

2. Heidenreich PA. Department of Veterans Affairs Quality Enhancement Research Initiative (QUERI) Chronic Heart Failure Strategic Plan, December 2009 (http://www.queri.research.va.gov/about/strategic_plans/chf.pdf accessed on March 5, 2011)

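### The blood draw fills only EDTA plasma tubes, but PIIINP and isoprostanes are specified in serum, so these two exploratory markers cannot be assayed as the protocol specifies

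*Combined protocol and SAP*

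**What the plan says.** All the relevant text on specimens is in the protocol, under *Baseline (randomization) visit*, in the paragraphs on fasting venipuncture and assays.

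- Volume: the draw is "for withdrawal of 20 cc of blood".
- Tubes: "The phlebotomist will draw two 10 ml EDTA plasma tubes for this protocol".
- Processing: one rule covers everything drawn, namely that "the blood tubes will be incubated at room temperature for 30 minutes before being spun in a centrifuge, aliquoted and frozen".
- PIIINP (printed in the protocol with an extra I): "Serum PIIIINP will be measured in [name] laboratory using a commercially available radioimmunoassay". The kit is then described as a "quantitative radioimmunoassay of intact aminoterminal propeptide of type III procollagen in human serum".
- Isoprostanes: "Serum isoprostanes will be measured in [name] laboratory using a commercially available ELISA".

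NT-proBNP is specified in plasma in the same paragraphs. No specimen type is given for TNF-alpha, IL-6 or hs-CRP. The *Final study visit* section repeats the baseline procedures, phlebotomy included, after 12 weeks. The *Statistical analysis* section treats the intermediate, mechanism-related measures as exploratory.

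**The concern.** The collection instruction and the assay instruction cannot both be followed. Staff who draw what the protocol tells them to draw will send the laboratory only plasma. A laboratory that runs what the protocol tells it to run needs serum for two of its assays.

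The markers at stake are PIIINP, which the protocol uses to follow connective tissue metabolism, and isoprostanes, the evident marker for the oxidative-stress mechanism set out in the background. If the conflict is left to local judgement, either the assays are run in a matrix that the plan does not declare, or someone adds or swaps a tube informally. In the second case the specimen type could differ between the two sites, or between a patient's two visits. A missed specimen cannot be collected afterwards. The section on protection against risks also says that leftover samples are destroyed once assayed, so an error found late may not be correctable.

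**Working it through.** The only arithmetic is volume and counts. The rest is a comparison of the text with itself.

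**1. Does the stated volume leave room for a serum tube?** Inputs: 2 tubes, 10 ml each, total 20 cc (venipuncture paragraph). 2 × 10 ml = 20 ml, which reproduces the protocol's total. Left for any other tube: 20 − 20 = 0 ml.

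**2. Which specimen does each marker call for, and is it drawn?**

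| Marker | Specimen named | Drawn? |
|---|---|---|
| PIIINP | serum (in the marker's name and in the kit description) | no |
| Isoprostanes | serum (in the marker's name only) | no |
| NT-proBNP | plasma | yes |
| TNF-alpha | none stated | cannot be judged |
| IL-6 | none stated | cannot be judged |
| hs-CRP | none stated | cannot be judged |

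Two of six markers have a named specimen that is not collected. Because the text names plasma for one marker and serum for two, the terms are not being used interchangeably.

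**3. Is a serum tube added elsewhere?** The list of study procedures in the overview mentions only a blood draw. The baseline visit text places the draw at the start of the visit without further detail. The final visit repeats the same phlebotomy. The section on protection against risks covers storage, shipping and destruction. None adds a tube.

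**4. Does the 30-minute room-temperature step supply serum?** No. It applies to the tubes that are drawn, and both are EDTA tubes. Standing does not turn an EDTA sample into serum.

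**5. How many patients and draws?** The draw belongs to the baseline visit, so it concerns randomized patients and not the approximately 500 screened. From *Sample size and power*: 39 + 39 + 20 = 98 patients. With two visits, at most 98 × 2 = 196 draws. With the evaluable numbers, 34 + 34 + 17 = 85 patients would have paired samples.

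**6. What would a mixed matrix do to the analysis?** The planned outcome is change from baseline, compared between arms. Suppose serum and plasma readings differ by an additive amount *d*, which the documents do not give. A patient measured in the same matrix at both visits has *d* cancel from the change. If a fraction *p* of an arm switches matrix between visits, that arm's mean change moves by *p* × *d*, and the contrast with control moves by (*p* active − *p* control) × *d*. The mix also adds variance *p*(1 − *p*)*d*² within the arm. With one matrix throughout, all these terms are zero.

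**The case against.** The strongest reply is that this may be a slip of one word per assay. The documents do not say that either kit rejects EDTA plasma. The PIIINP kit is described for human serum, which does not exclude plasma. For isoprostanes the only evidence is the word serum in front of the marker, with no description of the kit's matrix. If both kits work in EDTA plasma, nothing is lost except accuracy of labelling. All of this stands. A reader might infer that two biomarkers are lost to the trial; the documents do not support that, because they are silent on what the kits accept.

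A reader might also infer that the treatment comparison for these markers is biased. That does not follow either. The same draw is specified for all arms and both visits, so if the protocol's tubes are used throughout, each change is measured within one matrix. What stays open is whether the kits are valid in that matrix, and whether absolute values can be compared with other studies.

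The effect on the trial is also limited. The primary outcomes are LVEF and peak VO2, and the sample size rests on LVEF. The statistical section calls the mechanism analyses exploratory and tests secondary outcomes at 5% without multiplicity adjustment. It does not name PIIINP or isoprostanes, so their place among the mechanism measures is a reasonable inference and not a stated fact.

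Finally, phlebotomy is said to follow a separate written protocol, which is not among the documents and might name other tubes. If it does, it conflicts with the tube count and volume stated here, so the text would still need correction.

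**Conclusion.** The protocol contradicts itself. As written, PIIINP and isoprostanes, 2 of the 6 named blood markers, have no matching specimen at baseline or at the final visit in the roughly 98 randomized patients. They cannot be assayed as specified. Whether they can be assayed validly in what is collected is a question the documents leave open.

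The contradiction rests only on the protocol's own label for the tubes, the stated volume and the stated assay matrix. It does not depend on any assumption about the kits, and it is not an effect of redaction or text extraction, since the sentences are complete. Its reach is confined to exploratory markers: no primary estimate, significance level, power figure or sample size changes. It should be corrected because the samples are irreplaceable and the correction is cheap.

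**What to change.** Proceed in this order.

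1. Ask the laboratory whether the PIIINP and isoprostane kits are valid in EDTA plasma, and verify from site records which tubes have been used so far. The documents do not give enrolment status, so this must come before any tube change.
2. If both kits are valid in EDTA plasma, restate both assays as plasma assays and correct the description of the PIIINP kit's matrix. Collection does not change.
3. If either is not, replace one of the two 10 ml EDTA tubes with a serum tube, keeping the 20 ml total, and give the processing steps for each tube type. First check that the remaining plasma is enough for the other assays.
4. State that each patient's baseline and final samples are assayed in the same matrix. If some patients already have only EDTA baseline samples, do not form a change score from a plasma baseline and a serum final value.
5. State the specimen for TNF-alpha, IL-6 and hs-CRP in the same edit, since the plasma check in step 3 depends on it.

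Cost: a laboratory confirmation, a check of site records and a few lines of text. A tube swap keeps the draw volume but halves the blood collected for plasma, from 20 ml to 10 ml. The protocol gives no assay volumes, so whether 10 ml is enough cannot be judged from the documents.
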